### 7.1.1 Intent-to-Treat (ITT) Population

### 7.1.2 Per Protocol (PP) Population

#### 7.1.2.1 Safety (SAFT) Population

The SAFT Population will consist of all subjects in the No-Treatment control group, and all subjects in the Redensity treatment group that are randomized and received at least one treatment with a study device. Subjects in the SAFT Population will be analyzed in the group of the treatment they actually received, whether or not it is the group to which they are randomized.

## 8. SAMPLE SIZE JUSTIFICATION

The study will ensure that enrolled subjects are representative of U.S. population ethnicity and will be comprised of at least 25% subjects of Fitzpatrick skin IV to VI. In order to be able to detect a sufficient AE rate (i.e., maximum 2.5% in the sub-population of subjects of Fitzpatrick skin type IV to VI), the number of subjects must be increased beyond that required for achieving statistical power for the primary efficacy outcome; specifically:

## 9. STATISTICAL METHODS

### 9.1. Efficacy Analyses

#### 9.1.1 Primary Endpoint

The primary endpoint will be a co-primary endpoint. A responder will be defined as a subject who has a  $\geq 1$ -grade improvement on the **PR-SRS** as assessed by the **BLE** at Week 8 after initial or touch-up treatment, compared with the pre-treatment assessment (baseline) by the BLE. Only data from the first 8-week phase will be taken into account. The No-Treatment control group after treatment will not be pooled for the primary endpoint.

The effectiveness of TEOSYAL® RHA Redensity will be demonstrated if:

- The responder rate for subjects treated with TEOSYAL® RHA Redensity is statistically superior to the responder rate for the No-Treatment control , and;
- The responder rate for subjects treated with TEOSYAL® RHA Redensity is  $\geq 70\%$ , and;
- The difference between the responder rate for subjects treated with TEOSYAL® RHA Redensity and the No-Treatment group is  $\geq 50$  points.

### 9.1.2 Secondary Endpoints

Statistical inference tests will be performed using two-sided tests, with a 0.05 significance level. Data will be summarized descriptively. For the Secondary Endpoints, like for the Primary Endpoint, only data from the first 8 week phase will be taken into account, and will compare TEOSYAL® RHA Redensity to No-Treatment (the No-Treatment control group after treatment will not be pooled for the secondary endpoints):

- **FACE-Q** at Week 4 and Week 8 after initial or touch-up treatment.
- Proportion of subjects with a Global Aesthetic “improved” or “much improved”, as assessed by **subject** at Week 4 and Week 8 after initial or touch-up treatment, using the 5-grade Global Aesthetic Improvement (**GAI**) scale.
- Proportion of subjects with a Global Aesthetic “improved” or “much improved”, as assessed by **BLE** at Week 8 after initial or touch-up treatment, using the 5-grade Global Aesthetic Improvement (**GAI**) scale.
- Proportion of subjects “satisfied” or “very satisfied” at Week 8 after initial or touch-up treatment, using the 5-point scale assessing **Subject Satisfaction** with study treatment.

### 9.1.3 Exploratory Endpoints

For the following Exploratory Endpoints, like for the Primary Endpoint, only data from the first 8 week phase will be taken into account and will compare TEOSYAL® RHA Redensity to No-Treatment (the No-Treatment control group after treatment will not be pooled for these exploratory endpoints):

- Proportion of subjects with  $\geq 1$ -grade improvement from pre-treatment on the **PR-SRS** as assessed by the **Treating Investigator**, at Week 4 and Week 8 after initial or touch-up treatment, compared with the pre-treatment assessment (baseline) by the Treating Investigator.
- Proportion of subjects with  $\geq 1$ -grade improvement from pre-treatment on the **PR-SRS**, as evaluated by the Independent Photographic Reviewers (**IPR**) at Week 8 after initial or touch-up treatment, compared with the pre-treatment assessment (baseline) by the IPR. For a given subject to be considered a responder, at least 2 of the 3 readers must have confirmed a 1-point improvement for that subject.
- Proportion of subjects with a Global Aesthetic “improved” or “much improved”, as assessed by **Treating Investigator** at Week 4 and Week 8 after initial or touch-up treatment, using the 5-grade Global Aesthetic Improvement (**GAI**) scale.
- Proportion of subjects with  $\geq 1$ -grade improvement from pre-treatment of dynamic perioral rhytids on the 1-4 Modified **Glogau** classification of wrinkling as assessed by the **BLE** at

Week 8 after initial or touch-up treatment, compared with the pre-treatment assessment (baseline) by the BLE.

- Proportion of subjects with  $\geq 1$ -grade improvement from pre-treatment of dynamic perioral rhytids on the 1-4 Modified **Glogau** classification of wrinkling as assessed by the **Treating Investigator** at Week 4 and Week 8 after initial or touch-up treatment, compared with the pre-treatment assessment (baseline) by the Treating Investigator.

For the following Exploratory Endpoints, unlike for the Primary and Secondary Endpoints, data from the TEOSYAL® RHA Redensity group and from the No-Treatment control group after treatment will be pooled (if deemed comparable).

- Proportion of subjects with a  $\geq 1$ -grade improvement based on the **PR-SRS** assessed by the **BLE** at Weeks 8, 12, 16, 24, 36, and 52 after initial or touch-up treatment, compared with the pre-treatment assessment (baseline) by the BLE.
- Proportion of subjects with a  $\geq 1$ -grade improvement based on the **PR-SRS** assessed by the **Treating Investigator** at Weeks 4, 8, 12, 16, 24, 36, and 52 after initial or touch-up treatment, compared with the pre-treatment assessment (baseline) by the Treating Investigator.
- Proportion of subjects with a  $\geq 1$ -grade improvement, based on the **PR-SRS** as evaluated by the Independent Photographic Reviewers (**IPR**) at Week 8, 12, 16, 24, 36, and 52 after initial or touch-up treatment, compared with the pre-treatment assessment (baseline) by the IPR. For a given subject to be considered a responder, at least 2 of the 3 readers must have confirmed a 1-point improvement for that subject
- Proportion of subjects with  $\geq 1$ -grade improvement of their dynamic perioral rhytids on the 1-4 Modified **Glogau** classification of wrinkling as assessed by the **BLE** at Week 8, 12, 16, 24, 36, and 52 after initial or touch-up treatment, compared with the pre-treatment assessment (baseline) by the BLE.
- Proportion of subjects with  $\geq 1$ -grade improvement of dynamic perioral rhytids on the 1-4 Modified **Glogau** classification of wrinkling as assessed by the **Treating Investigator** at Week 4, 8, 12, 16, 24, 36, and 52 after initial or touch-up treatment, compared with the pre-treatment assessment (baseline) by the Treating Investigator.
- **FACE-Q** at Week 4, 8, 12, 16, 24, 36, and 52 after initial or touch-up treatment
- Proportion of subjects with a Global Aesthetic “improved” or “much improved”, as assessed by **subjects** at Week 4, 8, 12, 16, 24, 36, and 52 after initial or touch-up treatment, using the 5-grade Global Aesthetic Improvement (**GAI**) scale.
- Proportion of subjects with a Global Aesthetic “improved” or “much improved”, as assessed by **Treating Investigators** at Week 4, 8, 12, 16, 24, 36, and 52 after initial or touch-up treatment, using the 5-grade Global Aesthetic Improvement (**GAI**) scale.
- Proportion of subjects with a Global Aesthetic “improved” or “much improved”, as assessed by **BLE** at Week 8, 12, 16, 24, 36, and 52 after initial or touch-up treatment, using the 5-grade Global Aesthetic Improvement (**GAI**) scale.
- **Subject satisfaction** at Weeks 4, 8, 12, 16, 24, 36, and 52 after initial or touch-up treatment, using the 5-point scale assessing subjects’ satisfaction with study treatment.
- Proportion of subjects with a **natural look and feel**  $\geq 7$  assessed by subjects at Week 4, 8, 12, 16, 24, 36, and 52 after initial or touch-up treatment, using an 11-point scale.

## 9.2 Safety Analyses

[figure not shown]
[figure not shown]
Safety data will be presented as listings and summary tables based on the SAFT Population (unless otherwise specified).

### 9.3 General Statistical Considerations

### 9.3.1 Statistical Testing

For specific information regarding the statistical tests to be used in this study, please refer to [REDACTED] Statistical testing will be conducted using parametric and non-parametric processes as appropriate. Continuous variables that are normally distributed will be tested using the Student t-test, while testing will be conducted with the Mann-Whitney test if not normally distributed. Normality of the observed distribution will be confirmed using a Shapiro-Wilk test. Quantitative (i.e., nominal/categorical) variables in 2x2 tables will be tested using Fisher test. For larger tables (i.e., more than 2x2), Chi-2 test will be used if expected cell counts are all  $\geq 5$ .

All tests will be performed on a two-sided basis. A p-value of less than 5% will be considered statistically significant. First level risk error for secondary criteria will not be adjusted for multiplicity.

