Study Design	
This is a randomized, blinded, No-Treatment control, multicenter, prospective clinical study, to identify whether TEOSYAL® RHA Redensity is more effective than No-Treatment in the correction of moderate to severe perioral rhytids at Week 8 after last treatment.
 
The Treating Investigator (TI) at screening will evaluate the subject’s perioral rhytids severity using the Perioral Rhytids Severity Rating Scale (PR-SRS) for eligibility of the subject for the study.
 
The Blinded Live Evaluator (BLE) at screening will evaluate the subject’s perioral rhytids severity using the PR-SRS in order to confirm eligibility and to establish a pre-treatment score for assessment of effectiveness. This will be done independently of the TI, and exact concordance between the BLE and the TI is not necessary for eligibility of the subject for the study.
 
Enrolled subjects will be randomized to either the TEOSYAL® RHA Redensity treatment group or the “No-Treatment” control group. The TI will administer study device, and if necessary, subjects will receive a touch-up treatment 14 days following the initial treatment to optimize the results. The TI will conduct safety and effectiveness evaluations at study visits, which will occur at Week 4, 8, 12, 16, 24, 36, and 52 after the last treatment, and 4 weeks after a repeat treatment.
 
A Blinded Live Evaluator (BLE) will conduct assessments of efficacy during the trial, including assessment of the primary endpoint at Week 8 after the last treatment. The BLE will conduct effectiveness evaluations at Week 8, 12, 16, 24, 36, and 52 after the last treatment.
 
All subjects will be followed for 52 weeks after initial treatment or touch-up, at which point they will be offered retreatment (provided that the TI deems the treatment to be appropriate and the subject agrees) and will then be followed for 4 weeks after retreatment before exiting the study. If a subject has returned to his pre-treatment PR-SRS score at Week 12 or Week 16 or Week 24 or Week 36 after initial treatment or touch up (as assessed by the TI), subject will be eligible for optional early retreatment if necessary at 12 or 16 or 24 or 36 weeks after baseline (provided that the TI deems the treatment to be appropriate, and the subject agrees). The subject will then be
		

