11.2 Secondary Endpoints

For the Secondary Endpoints, like for the Primary Endpoint, only data from the first 8 week phase will be taken into account, and will compare TEOSYAL® RHA Redensity to No-Treatment (the No-Treatment control group after treatment will not be pooled for the secondary endpoints):

- FACE-Q at Week 4 and Week 8 after initial or touch-up treatment.
- Proportion of subjects with a Global Aesthetic “improved” or “much improved”, as assessed by subject at Week 8 after initial or touch-up treatment, using the 5-grade Global Aesthetic Improvement (GAI) scale.
- Proportion of subjects with a Global Aesthetic “improved” or “much improved”, as assessed by BLE at Week 8 after initial or touch-up treatment, using the 5-grade Global Aesthetic Improvement (GAI) scale.
- Proportion of subjects “satisfied” or “very satisfied” at Week 8 after initial or touch-up treatment, using the 5-point scale assessing subjects’ satisfaction with study treatment.

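### In the readable SAP text FACE-Q at Weeks 4 and 8 is compared with no baseline term; unless the redacted test table says otherwise, ANCOVA would give a more precise estimate

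*SAP*

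**What the plan says.** - **Test rule.** SAP 9.3.1 states: "Continuous variables that are normally distributed will be tested using the Student t-test". Otherwise, "testing will be conducted with the Mann-Whitney test if not normally distributed". The choice is made from the data: "Normality of the observed distribution will be confirmed using a Shapiro-Wilk test". On level and sidedness: "All tests will be performed on a two-sided basis" and "A p-value of less than 5% will be considered statistically significant".
- **Deferral.** The same section opens its rule with "For specific information regarding the statistical tests to be used in this study, please refer to", and the target of that reference is redacted. The tables in SAP Appendix A (Summary of Statistical Tests) are blacked out too.
- **Endpoint.** Protocol 11.2 lists "FACE-Q at Week 4 and Week 8 after initial or touch-up treatment" as a secondary endpoint comparing the device with No-Treatment, and SAP 9.1.2 repeats it. The entry mentions no baseline, no change score and no model. By contrast, the PR-SRS responder endpoint (SAP 9.1.1) and the Glogau endpoints (SAP 9.1.3) are explicitly defined against the pre-treatment assessment.
- **Available baseline.** The Protocol Synopsis (Study Design) has the BLE grade PR-SRS at screening "to establish a pre-treatment score for assessment of effectiveness". That score defines the primary responder. No readable text uses it for FACE-Q.
- **Other model terms.** No ANCOVA, regression or covariate appears in the readable text. SAP 9.3.7 pools centres, and SAP 9.3.8 uses baseline characteristics only to judge pooling of the two countries. SAP 9.3.3 lists a 95% confidence interval among the descriptive statistics by group; no interval for a between-arm difference is visible.

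**The concern.** A two-sample test on a follow-up score leaves in the error term all the between-subject variation that a baseline score would explain. With 3:1 allocation and about 50 controls, the control arm dominates the standard error, so this variation costs more than it would in a balanced trial of the same size. A baseline covariate recovers part of it without recruiting anyone.

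What is at stake is the width of the interval around the FACE-Q effect and, if that effect is modest, the power to show it. The decision on effectiveness is not at stake: none of the three co-primary criteria in SAP 9.1.1 involves FACE-Q.

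**Working it through.** **Inputs from the documents.** At least 200 randomised, 150 to the device and 50 to No-Treatment (Protocol 4.2.1); 3:1 ratio (SAP 4); dropout up to 20% (SAP 9.3.5); two-sided 5% (SAP 9.3.1).

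**Assumed, because not given.** Correlation r between baseline and follow-up FACE-Q of 0.3, 0.5 or 0.7; equal SD at baseline and follow-up; for the power example, a true difference of 0.4 SD. No FACE-Q effect size, SD or power statement is readable.

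**The plan's own figure.** The Protocol Synopsis (Sample Size) inflates 160 for 20% dropout: 160 / 0.8 = 200, which reproduces. At 3:1 this is 150 and 50. The calculation is driven by adverse event detection, not by FACE-Q.

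**Step 1, unadjusted standard error.** SE = √(1/150 + 1/50) = 0.163 SD.

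**Step 2, relative variance.** Against a t-test on follow-up scores (set to 1), a t-test on change has variance 2(1 − r) and ANCOVA has 1 − r². The ratio of ANCOVA to change is (1 − r²) / [2(1 − r)] = (1 + r)/2. The cut in standard error is 1 minus the square root of the relevant ratio.

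| | r = 0.3 | r = 0.5 | r = 0.7 |
|---|---|---|---|
| Variance, change-score t-test | 1.40 | 1.00 | 0.60 |
| Variance, ANCOVA | 0.91 | 0.75 | 0.51 |
| ANCOVA SE (SD units) | 0.156 | 0.141 | 0.117 |
| SE cut against follow-up test | 5% | 13% | 29% |
| SE cut against change test | 19% | 13% | 8% |
| Equivalent unadjusted N, 200/(1 − r²) | 220 | 267 | 392 |

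The equivalent N is relative to the follow-up-score test.

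**Step 3, detectable difference at 80% power.** (1.960 + 0.842) × SE. Unadjusted on follow-up scores: 0.457 SD. ANCOVA: 0.436, 0.396 or 0.327 SD. If the full 20% dropout had already occurred by Week 8 (120 v 40, a worst case), the unadjusted value is 0.511 SD and ANCOVA gives 0.488, 0.443 or 0.365 SD.

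**Step 4, power at 0.4 SD.** Normal approximation, Φ(0.4/SE − 1.960). Unadjusted on follow-up scores: 0.4/0.1633 − 1.960 = 0.49, so 69%. ANCOVA: 73%, 81% or 93%. At an assumed 1.0 SD, unadjusted power already exceeds 99.9%, even with 120 v 40.

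**Step 5, chance imbalance.** The baseline difference between arms falls within ±1.96 × 0.163 = ±0.32 SD in 95% of randomisations. A follow-up-score test carries r times it into the estimate (±0.10, ±0.16 or ±0.22 SD). A change-score test carries (1 − r) times it, in the opposite direction (±0.22, ±0.16 or ±0.10 SD). This is already inside the standard error of Step 1. It describes the same loss as Step 2 and must not be added to it.

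The figures concern comparisons of means and ignore the degree of freedom spent on each covariate, which is negligible at this size. They were not worked out for the Mann-Whitney branch.

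**The case against.** The strongest objection is redaction. SAP 9.3.1 is a general section that points elsewhere for the specific tests, and the places where a FACE-Q analysis would be expected (SAP Appendix A, SAP 6.1, Protocol 9.5 and 11.7) cannot be read. A reader might infer that the plan omits baseline adjustment for FACE-Q altogether. The documents do not support that: Appendix A may name an adjusted model, and a t-test on change from baseline would fit the same sentence in 9.3.1 while using the baseline. This stands, and it makes the point conditional. It does not remove the point, because the readable rule names only covariate-free tests, and at every correlation examined ANCOVA is more precise than either unadjusted form.

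A reader might also infer that chance imbalance biases the result. It does not. Under randomisation the unadjusted difference is unbiased and its type I error is valid.

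Nor can it be said that the baseline BLE PR-SRS goes unused, since it defines the primary responder. It is only not visibly used for FACE-Q.

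Two further limits stand. Every figure assumes a baseline FACE-Q whose collection cannot be confirmed. And FACE-Q is a secondary endpoint: if the effect against No-Treatment is large, the test result will not depend on adjustment, although the interval would still be narrower.

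**Conclusion.** The point holds as a conditional improvement in efficiency of minor weight. In the readable text, the only tests named for a continuous endpoint carry no covariate, and the FACE-Q entry names no baseline term. If the redacted table does not already specify an adjusted model, and if FACE-Q is completed before first treatment, ANCOVA would shorten the standard error by 5% to 29% against a follow-up-score test, or by 8% to 19% against a change-score test, over assumed correlations of 0.3 to 0.7. If no baseline FACE-Q exists, only the BLE PR-SRS grade is known to be available. The gain from it is then smaller and cannot be quantified from the documents. Validity, type I error and the co-primary criteria are not in question.

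**What to change.** Unless Appendix A already does so, add to SAP 9.1.2 wording such as:

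> FACE-Q at Week 4 and at Week 8 will each be analysed by ANCOVA with treatment arm, baseline FACE-Q and baseline BLE PR-SRS as terms. The adjusted difference will be reported with its 95% confidence interval. The two-sample test of Section 9.3.1 will be supportive.

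If FACE-Q is not collected before first treatment, drop that term and adjust for baseline BLE PR-SRS alone. If Appendix A does name an adjusted model, it is enough to make 9.3.1 agree with it. Either way the model should be fixed before unblinding, in keeping with the SAP's stated aim of specifying methods before database lock.

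The cost is the wording and one extra model per visit, with no more subjects and no new data if a baseline FACE-Q is already collected. The downside is reliance on a linear model for a bounded score, which is a reason to keep the planned two-sample test alongside it.

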#### **4. TREATMENT ALLOCATION AND RANDOMIZATION**

Upon qualifying for treatment, subjects will be randomized to a study group utilizing a randomization algorithm embedded into the electronic Case Report Form (eCRF). Subjects will be randomized (3:1 ratio) to one of the following groups:

- TEOSYAL® RHA Redensity;
- No-Treatment (untreated control).

Subjects will be considered “enrolled” at the time of consent, and will be considered “enrolled and randomized” at the time of randomization. The required sample size is based on “enrolled and

randomized" subjects. If an enrolled subject withdraws from the study prior to being randomized, he/she may be replaced.

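### With 3:1 allocation, the SAP's general rule of Student's t-test or Mann-Whitney leaves the FACE-Q comparison exposed if the arms differ in spread; naming Welch's t-test removes the exposure at almost no cost (minor)

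*SAP*

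**What the plan says.** SAP 9.3.1 gives the general rule for continuous variables: "Continuous variables that are normally distributed will be tested using the Student t-test". Those found not to be normal go to Mann-Whitney instead. The choice between them is made on the data: "Normality of the observed distribution will be confirmed using a Shapiro-Wilk test". The section does not give the level of that check, and it does not say whether the check applies within each arm or to the combined sample. The readable text contains no unequal-variance version of the t-test and no check of variances. On error rates it says "All tests will be performed on a two-sided basis" and "A p-value of less than 5% will be considered statistically significant". SAP 9.3.1 and 9.3.6 apply no multiplicity adjustment to secondary endpoints.

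Allocation is unequal. SAP section 4 says "Subjects will be randomized (3:1 ratio) to one of the following groups", and Protocol 4.2.1 sets minimum arms of 150 treated and 50 untreated.

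The endpoint this bears on is in Protocol 11.2 (and SAP 9.1.2): "FACE-Q at Week 4 and Week 8 after initial or touch-up treatment", compared between the treated arm and the No-Treatment arm. The other three secondary endpoints are proportions.

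SAP 9.3.1 opens with a pointer, "For specific information regarding the statistical tests to be used in this study, please refer to", whose target is redacted. The tables in Appendix A (summary of statistical tests) are redacted too, so the test named specifically for FACE-Q cannot be read.

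**The concern.** The pooled t-test estimates one common variance, weighted by arm size. At 3:1 that estimate is dominated by the treated arm, while the uncertainty in the mean difference comes mostly from the smaller control arm. If the control arm is the more variable one, the standard error is too small and the test rejects too often. If the treated arm is the more variable one, the standard error is too large and power is lost. Confidence intervals inherit the same fault when there is a real effect.

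A difference in spread is possible here because only one arm is treated. Varying response could widen the treated arm, and scores crowding toward the top of the scale could narrow it. The Shapiro-Wilk check does not guard against either, because two normal samples with different SDs can both pass it.

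The rule also leaves open what is estimated. Student's test addresses a mean difference, and Mann-Whitney addresses a difference in distributions and supplies no mean difference. At stake are the p-values and intervals for one listed secondary endpoint at two visits.

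**Working it through.** **Inputs from the documents.** Two-sided 5% (SAP 9.3.1 and 9.1.2); 3:1 allocation (SAP 4); at least 150 and 50 (Protocol 4.2.1); dropout up to 20% (SAP 9.3.5); secondary endpoints analysed on observed data (Protocol 11.6).

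**The plan's own figure.** The only readable sample-size derivation (Protocol synopsis) is 160 / 0.8 = 200. It reproduces, and 3:1 of 200 is 150:50. With 20% dropout the arms are 150 × 0.8 = 120 and 50 × 0.8 = 40. No SD, effect size or power for FACE-Q is given, so there is no FACE-Q figure to reproduce.

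**Assumptions.** SD ratio treated/control r from 0.5 to 2; Student's test read as pooled-variance; Shapiro-Wilk at 0.05, run both within arm and on the combined sample.

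**Formula.** Take the control SD as 1.
- True variance of the mean difference: V = r²/150 + 1/50.
- Variance that the pooled test uses, on average: P = [(149r² + 49)/198] × (1/150 + 1/50).
- Large-sample error rate at equal means: 2 × [1 − Φ(1.96 × √(P/V))].

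Worked case, r = 0.5 (control SD twice the treated SD): V = 0.25/150 + 0.02 = 0.02167. P = (37.25 + 49)/198 × 0.02667 = 0.01162. P/V = 0.536 and √ = 0.732. 1.96 × 0.732 = 1.435, so the error rate is 0.151.

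Worked case, r = 1.5: V = 0.035, P = 0.05175, P/V = 1.479 and √ = 1.216. 1.96 × 1.216 = 2.383, so the error rate is 0.017.

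**Results at 150:50, normal data, equal means.** The simulations used 10,000 trials per setting, so the simulation standard error near 0.05 is about 0.002. A dash means not simulated.

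| SD ratio treated/control | Pooled t (formula) | SAP rule, check within arm | SAP rule, check on combined sample | Welch |
|---|---|---|---|---|
| 0.5 | 0.151 | 0.150 | 0.105 | 0.050 |
| 0.67 | 0.106 | 0.106 | 0.093 | 0.050 |
| 0.8 | 0.079 | 0.074 | 0.072 | 0.048 |
| 0.9 | 0.063 | – | – | – |
| 1 | 0.050 | 0.047 | 0.046 | 0.046 |
| 1.1 | 0.040 | – | – | – |
| 1.25 | 0.029 | 0.029 | 0.028 | 0.048 |
| 1.5 | 0.017 | 0.014 | 0.013 | 0.046 |
| 2 | 0.0075 | 0.010 | 0.010 | 0.050 |

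- At 120:40 the formula values are the same to within 0.0002.
- At 100:100 every ratio gives 0.050, so the unequal allocation is what turns unequal spread into a size error.
- Mann-Whitney alone on normal data gives 0.099 at ratio 0.5 and 0.020 at ratio 2.
- With moderately skewed data (gamma, shape 4) at 150:50, the check selects Mann-Whitney in at least 98% of trials. Rejection at equal means is then 0.21, 0.12, 0.080, 0.053, 0.049, 0.068 and 0.11 at ratios 0.5, 0.67, 0.8, 1, 1.25, 1.5 and 2. Welch on skewed data stays at 0.047-0.056 across both sample sizes.

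**Intervals under a real effect** (true mean difference 1, 150:50, 20,000 trials). The nominal 95% pooled interval covers about 89.5% when the control SD is 1.5 times the treated SD, and about 98% in reverse. Welch covers about 95% in both.

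**The case against.** The strongest objection is that the FACE-Q test is not visible. SAP 9.3.1 defers to a redacted source, the Appendix A tables are blacked out, and a single named FACE-Q analysis may already be there. That stands, so the point rests on the readable general rule. That Student's test means the pooled form is an inference from the name, and so is treating FACE-Q as a continuous variable under this rule.

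A reader might infer that FACE-Q p-values are wrong whenever the arms differ in spread. The figures do not support that. A 10% SD difference moves 5% only to 6.3% or 4.0%, and one unequal-spread case (skewed data, ratio 1.25) stays at 4.9%. For normal data the error is conservative when the treated arm is the more variable one.

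A reader might also infer that the 5% rate is already known to fail for FACE-Q. It is not. If treatment changes nothing for anyone, randomisation gives both arms the same distribution, and the rule holds about 5% (0.046-0.053 at ratio 1). The inflated figures need a treatment that changes the spread but leaves the mean unchanged. The interval-coverage result does not need that special case, which is why the point survives.

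Nor is the normality check shown to do harm of its own. On normal data with unequal SDs, the gated error rates are close to Student's alone, or nearer to 5%. Its weakness is that it does not look at variance and leaves the estimated quantity open. Mann-Whitney tests a different null, so some of its rejections at equal means with skewed data reflect real distributional differences and not faulty p-values.

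Finally, effectiveness is decided only by the three responder-rate criteria in SAP 9.1.1. FACE-Q is one unadjusted secondary endpoint. That stands and limits the severity.

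**Conclusion.** The concern holds as a conditional and minor one. Under the readable rule and 3:1 allocation, the FACE-Q comparison can be mis-sized if the arms differ in spread. For normal data with equal means the error rate is about 10-15% if the control SD is 1.5 to 2 times the treated SD, about 1-2% in the opposite direction, and about 6% or 4% for a 10% difference. Pooled intervals are too narrow or too wide in the same way when there is a real effect.

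This rests on assumed SD ratios, on the pooled reading of Student's test, and on Appendix A not already naming another FACE-Q analysis. The documents give no FACE-Q SDs, so neither the actual size nor the direction of the distortion can be stated. The primary endpoint is not affected.

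**What to change.** First check the unredacted Appendix A. If it does not already do so, name Welch's unequal-variance t-test, with mean difference and 95% CI, as the single FACE-Q analysis at Week 4 and at Week 8. State that it is not selected by a normality pre-test. Keep Mann-Whitney as a sensitivity analysis.

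If a baseline FACE-Q score is collected, which the readable text does not establish, ANCOVA on baseline score and arm with heteroscedasticity-robust standard errors is an option.

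The cost is SAP wording, with no new data. When the SDs are equal, Welch loses about 0.5 percentage points of power and its coverage is essentially the same as the pooled interval's.

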### **9.3.6 Multiple Comparisons**

No methods will be used to accommodate multiplicity (unless otherwise specified).

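### Six secondary comparisons are each tested at two-sided 0.05, with no multiplicity adjustment and, in the legible text, no order and no condition on the primary result.

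*SAP*

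**What the plan says.** SAP 9.1.2 makes the secondary comparisons inferential: "Statistical inference tests will be performed using two-sided tests, with a 0.05 significance level". SAP 9.3.1 sets the label, "A p-value of less than 5% will be considered statistically significant", and then says of the secondary criteria: "First level risk error for secondary criteria will not be adjusted for multiplicity". SAP 9.3.6 applies the same approach generally: "No methods will be used to accommodate multiplicity (unless otherwise specified").

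Protocol 11.2 and SAP 9.1.2 list four secondary measures of TEOSYAL RHA Redensity against no treatment in the first 8-week phase:

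- FACE-Q, in both documents: "FACE-Q at Week 4 and Week 8 after initial or touch-up treatment".
- Subject GAI. The Protocol has one visit: "as assessed by subject at Week 8 after initial or touch-up treatment, using the 5-grade Global Aesthetic Improvement (GAI) scale". The SAP has two: "at Week 4 and Week 8 after initial or touch-up treatment, using the 5-grade Global Aesthetic Improvement".
- BLE GAI, in both documents: "as assessed by BLE at Week 8 after initial or touch-up treatment, using the 5-grade Global Aesthetic Improvement (GAI) scale".
- Satisfaction at Week 8, in both documents.

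That is six comparisons in the SAP and five in the Protocol. SAP section 1 says that the SAP governs where the two differ, so the operative count is six.

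SAP 9.1.1 defines effectiveness by three conditions that must all hold: statistical superiority on the BLE-rated PR-SRS responder rate, a treated responder rate of at least 70%, and a difference of at least 50 points. SAP 1.1 describes the trial as pivotal and intended to support a PMA.

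**The concern.** The secondary analyses are not presented as descriptive. Each one is a test that earns the label of statistical significance below 5%. With six such tests and no adjustment, the chance that at least one crosses the line by luck is well above 5%.

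A primary gate matters more here than in many trials, because the primary criterion includes two point-estimate thresholds. The trial can show superiority and still miss the 70% or the 50-point requirement. On the legible text, all six secondary comparisons could then still be reported as significant.

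Order also matters. The control is no treatment, and the BLE is the only assessor whom the Protocol synopsis describes as blinded to allocation. One of the six comparisons, BLE GAI at Week 8, is rated by that assessor. The plan gives it no priority over measures from subjects who know whether they were injected.

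**Working it through.** **The plan's own figure.** The documents state no familywise error rate. The related figure is the sample size in the Protocol synopsis: 160 / 0.8 = 200, which reproduces. At 3:1 this gives 150 and 50. With 20% lost it gives 0.8 × 150 = 120 and 0.8 × 50 = 40. The 20% is stated for the whole study, so 120 and 40 are cautious for Week 8.

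**Any false positive, all six nulls true, two-sided 0.05 each.**

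- Six independent tests: 1 − 0.95^6 = 1 − 0.7351 = 26.5%.
- The Protocol's five: 1 − 0.95^5 = 1 − 0.7738 = 22.6%.
- Bound for six under any dependence: 6 × 0.05 = 30%.

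**False positive in the device's favor.** Each test contributes 0.025: 1 − 0.975^6 = 14.1% under independence.

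**Correlated tests.** The six comparisons use the same subjects, so positive correlation is likely. With a common correlation among normal test statistics (an assumption, since the documents give none):

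| Correlation | Either direction | In the device's favor |
|---|---|---|
| 0 | 26.5% | 14.1% |
| 0.3 | 24.1% | 12.2% |
| 0.5 | 20.7% | 10.4% |
| 0.7 | 16.4% | 8.2% |
| 0.9 | 10.8% | 5.4% |

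**Effect of the Fisher test.** SAP 9.3.1 uses Fisher's test for 2×2 tables, which covers four of the six. Its exact size at 150 vs 50 is 3.1% to 4.2% for common rates of 5% to 50%. Using 4.2% for those four and 5% for the two FACE-Q tests, under independence: 1 − 0.95^2 × (1 − 0.042)^4 = about 24%.

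**Cost of a fixed sequence.** This depends on effect sizes that the documents do not give, so the following are assumptions. Power is for a single test:

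| Assumed effect | 120 vs 40 | 150 vs 50 |
|---|---|---|
| 50% vs 10% (Fisher) | 99.9% | 99.99% |
| 60% vs 20% (Fisher) | 99.6% | 99.9% |
| 50% vs 20% (Fisher) | 93.6% | 97.5% |
| 40% vs 20% (Fisher) | 63% | 74% |
| FACE-Q, standardized difference 0.8 | 99.2% | 99.8% |
| FACE-Q, standardized difference 0.5 | 78% | 86% |

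If the six tests were independent with equal power, the chance that all pass in sequence is power^6: 0.99^6 = 94%, 0.95^6 = 74%, 0.80^6 = 26%.

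**Cost of the gate.** At 150 vs 50, the two point-estimate criteria are both met with probability 54% at true rates of 70% vs 10%, 76% at 75% vs 20%, and 99.8% at 80% vs 10%.

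**The case against.** The best defense has four parts.

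**The all-null case is remote once the primary succeeds.** A device with at least 70% responders and a 50-point difference is unlikely to do nothing on every secondary measure. This stands. It means that the risk lies mainly in a trial that fails its primary, and that the gate does more work than the ordering.

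**The plan is open about it.** The tests are declared unadjusted, and effectiveness is defined by the primary criteria alone. A reader might infer that a significant secondary result could rescue a failed trial. The documents do not support that, and no legible section says that secondary results will carry claims. What remains is that the label of significance is available regardless of the primary result.

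**Redaction.** A reader might infer that the plan contains no gate at all. Protocol 11.7 and SAP Appendix A are blacked out, and SAP 9.3.6 allows for exceptions, so only the legible text can be said to lack a gate or an order. The sentence in SAP 9.3.1 on secondary criteria is legible and specific, so a hidden adjustment would contradict it. A hidden gate or order need not.

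**The numbers can be overread in both directions.** A reader might take 26% as a ceiling. It is the independence value, the bound is 30%, and the likely figure is lower because the measures are probably correlated. About half of the error under independence favors no treatment. A reader might also infer that a fixed sequence is nearly free. That holds only for large effects, and the documents give no secondary effect sizes.

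**Conclusion.** The point holds as a cheap improvement to the SAP. It does not touch the primary conclusion. Six comparisons are tested at two-sided 0.05 without adjustment, and no order or primary gate is legible.

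If all six nulls are true, the chance of at least one nominally significant result is 26.5% under independence, about 11% to 24% at correlations of 0.9 to 0.3, and never above 30%. In the device's favor it is 14% under independence and about 5% to 12% at those correlations.

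These figures assume one FACE-Q score per visit. The legible text does not say how many FACE-Q scales are tested, and more than one would enlarge the family. The issue has practical weight only if secondary results are to be used as confirmatory claims, which the legible text leaves open.

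**What to change.** Before database lock and unblinding, revise SAP 9.3.1 and 9.3.6 to say:

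1. Formal secondary testing starts only if all three primary criteria in SAP 9.1.1 are met.
2. It then proceeds in a fixed sequence, each test at two-sided 0.05, led by the masked measure. For example: BLE GAI Week 8, FACE-Q Week 8, subject GAI Week 8, satisfaction Week 8, FACE-Q Week 4, subject GAI Week 4.
3. P-values after the first non-significant test are labelled nominal, as are all secondary p-values if the primary fails.

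This holds familywise error for the secondary family to at most 5%. If no secondary claims are intended, a single sentence labelling all secondary p-values nominal is enough.

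In either case, reconcile subject GAI at Week 4 between Protocol 11.2 and SAP 9.1.2, because it sets the family at six or five. If FACE-Q has more than one scale, name the one that enters the sequence.

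The change is to wording only, with no new data, visits or subjects. The downside is that one failure ends formal claims for every later endpoint. The loss is small if differences are about 40 points (Fisher power above 99% at 120 vs 40). It is not small if they are about 20 points (63% for 40% vs 20%). The sponsor should choose the order with its own expected effects in view.
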